11.2 Sample Size Considerations

The primary analysis will compute the proportion of ciprofloxacin-susceptible *N. gonorrhoeae*-infected subjects with microbiological cure 5-10 days after receiving ciprofloxacin in the PP analysis population. The confidence interval for the microbiological cure proportion will be computed using a one-sided modified Jeffreys interval using a significance level of 0.05. Power calculations were performed via a simulation study based on 10,000 replications assuming a 98% microbiological cure rate.

Figure 11.2 below presents the power available to test that the microbiological cure rate is at least 95% (i.e., lower bound of the one-sided confidence interval is at least 95%) across a range of evaluable sample sizes. Here, evaluable denotes eligible for the PP analysis population. The power reaches 80% at a sample size of 195 evaluable subjects; however, since the power curve is not monotonic, sample sizes directly on either side of 195 are below 80%. Since the exact number of evaluable subjects at the end of the study is difficult to predict, an evaluable target of 257 subjects is chosen to ensure at least 80% even if the exact number of evaluable subjects at the end of the study differs

slightly from 257. With a target of 257, the power available is approximately 85% and we can fall at most 10 subjects short (sample size of 247 evaluable subjects) and still ensure 80% power. Any sample size greater than 257 will ensure at least 80% power.

Figure 11.2: Power Available to Test That the Microbiological Cure Rate Is at Least 95%

To calculate the number of subjects required to enroll to reach 257 subjects in the PP analysis population, the following assumptions are made:

- 25% of enrolled subjects will be culture negative at baseline.
- 10% of subjects will be excluded from the PP analysis population (reasons for exclusion are stated in section 11.4.1)

Under these assumptions, enrolling 381 subjects will provide 257 subjects in the PP analysis population. Since the proportion of subjects who will be culture negative at baseline can vary depending on a number of factors, 25% is a rough estimate. The exact number of subjects needed to provide 257 subjects in the PP analysis population may vary from 381, so 381 is an approximate enrollment target.

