11.4.1 Analysis Populations

Per-Protocol (PP) Population: This analysis population includes enrolled subjects who met all inclusion/exclusion criteria, have *N. gonorrhoeae* isolated on Day 1 culture from the rectum or urogenital site, have an evaluable microbiological outcome status (see section 11.4.3.1), complied with study treatment, did not receive any contraindicated medication or systemic antibiotic other than the study medication for any concomitant infection prior to Visit 2 (Day 5-10), and returned for their Visit 2 (Test of Cure) visit within window.

To be compliant with study treatment, a subject must be able to swallow the pill and not vomit within 1 hour of administration.

For the primary analysis, subjects need only have *N. gonorrhoeae* isolated on Day 1 culture from the rectum or urethra (male) or cervix/vagina (female). For the analysis of secondary objective 1, subjects need to have *N. gonorrhoeae* isolated on Day 1 culture at the particular site being assessed.

In addition, alternate per-protocol analyses which exclude subjects with reported concomitant infection/disease/procedure that may interfere with study product, use of concomitant medications or products that may interfere with study product, significant protocol deviations, and other events that may impact study product

effectiveness or study analyses will be explored. Details will be described in the separate statistical analysis plan.

Microbiological Intent-to-Treat (micro-ITT) Population: This analysis population includes all enrolled subjects who have *N. gonorrhoeae* isolated from the rectum or urogenital site on Day 1 culture.

For the primary analysis, subjects need only have *N. gonorrhoeae* isolated on Day 1 culture from the rectum or urethra (male) or cervix/vagina (female). For the analysis of secondary objective 1, subjects need to have *N. gonorrhoeae* isolated on Day 1 culture at the particular site being assessed.

Intent-to-Treat (ITT) Population: This analysis population includes all enrolled subjects.

Subjects who receive any treatment other than the study medication for their *N. gonorrhoeae* infection will be included in all efficacy analyses as treatment failures.

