3.3.2. Microbiological Outcome Status

- 1 Microbiological outcome status for the primary analysis is evaluated at Visit 2 and is defined as follows:
 - Microbiological Cure: *N. gonorrhoeae* not detectable by culture from all anatomical sites that had detectable *N. gonorrhoeae* at Visit 1.
 - Microbiological Failure: *N. gonorrhoeae* detectable by culture from at least one anatomical site that had detectable *N. gonorrhoeae* at Visit 1.
 - Non-evaluable: At least one of the following:
 - Subject did not return for Visit 2, or
 - Culture results at Visit 2 were not available for any reason, or
 - Subject could not be evaluated for microbiological outcome status for any other reason.
- 2 For the analysis of secondary objective 1, microbiological outcome status at each anatomical site is evaluated at Visit 2 and is defined for a particular anatomical site as follows:
 - Microbiological Cure: *N. gonorrhoeae* not detectable by culture at the particular anatomical site that had detectable *N. gonorrhoeae* at Visit 1.
 - Microbiological Failure: *N. gonorrhoeae* detectable by culture at the particular anatomical site that had detectable *N. gonorrhoeae* at Visit 1.
 - Non-evaluable: At least one of the following:
 - Subject did not return for Visit 2, or
 - Culture results at Visit 2 were not available for any reason, or
 - Subject could not be evaluated for microbiological outcome status for any other reason.

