6.3.2.2. Microbiological Intent-to-Treat (micro-ITT) Population

For the primary analysis, the micro-ITT population includes all enrolled subjects who have wild type *gyrA* serine 91 *N. gonorrhoeae* isolated from the rectum or urogenital site on Day 1 culture. Subjects with infections at multiple anatomic sites are included as long as one of the infected sites is the rectum or urogenital site. Subjects with infections at multiple anatomic sites must be wild-type at each culture-positive site to be included in the primary analysis.

Subjects with non-evaluable outcome status will be included in the micro-ITT population and classified as microbiological failures. Subjects who discontinued early from the study with lack of treatment effect being the documented reason for discontinuation will be included as microbiological failures. Subjects who vomited within 1 hour of administration will be included as microbiological failures.

For the analysis of secondary objective 1, subjects need to have wild type *gyrA* serine 91 *N. gonorrhoeae* isolated on Day 1 culture at the particular anatomical site being assessed. The results at the other anatomical sites will not be considered when determining a subject's eligibility into each of the site-specific populations.

There will be four micro-ITT populations identified:

- Primary micro-ITT population
- Rectal micro-ITT population
- Urogenital micro-ITT population
- Pharyngeal micro-ITT population

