6.3.2.3. Per Protocol Population

For the primary outcome measure, the PP population includes enrolled subjects who met all inclusion/exclusion criteria, have wild type *gyrA* serine 91 *N. gonorrhoeae* isolated on Day 1 culture from the rectum or urogenital site, have an evaluable microbiological outcome status (see Section 3.3.2), complied with study treatment, did not receive any contraindicated medication or systemic antibiotic other than the study medication for any infection prior to Visit 2, and returned for their Visit 2 (Test of Cure) visit within window. Subjects with infections at multiple anatomic sites are included as long as one of the infected sites is the rectum or urogenital site.

In addition, subject who are infected at multiple anatomic sites must meet either of the two following criteria to be included in the PP population:

- wild-type at each culture positive site, or
- wild-type at the rectum/urogenital site and unknown *gyrA* status at the pharyngeal site (due to indeterminate or missing result).

For subjects who meet the second criteria above, the pharyngeal results will be ignored in the determination of cure status.

For the PP analysis population, subjects with non-evaluable outcome status will be excluded from the analysis. Subjects who discontinued early from the study with lack of treatment effect being the documented reason for discontinuation will be included as microbiological failures.

For the analysis of secondary objective 1, subjects need to have wild type *gyrA* serine 91 *N. gonorrhoeae* isolated on Day 1 culture at the particular anatomical site being assessed. In addition, alternate per-protocol analyses which exclude subjects with reported concomitant infection/disease/procedure that may interfere with study product, use of concomitant medications or products that may interfere with study product, significant protocol deviations, and other events that may impact study product effectiveness or study analyses will be explored. Exclusions from this alternate PP population will be determined on a case-by-case basis prior to database lock.

There will be four PP populations and identified based on wild type *gyrA* serine 91 *N. gonorrhoeae* isolation at Day 1 for a particular site. The results at the other anatomical sites will not be considered when determining a subject's eligibility into each of the site-specific populations.

- Primary PP population
- Rectal PP population
- Urogenital PP population

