8.1.1. Sensitivity Analyses

A sensitivity analysis of the primary outcome will be performed to assess the impact of the choice of confidence interval. The primary analysis will be repeated using three different kinds of confidence intervals for binomial proportions: Wilson, Agresti-Coull, and Blaker intervals [2]. The summary of microbiological cure number, microbiological cure rate, and one-sided 95% confidence intervals by analysis population will be presented. See Table 9.

Additional sensitivity analyses of the primary outcome measure will be performed with modifications to the definition of the micro-ITT and PP populations. First, the micro-ITT and PP populations will be modified such that subjects with culture-positive but unknown (indeterminate or missing) *gyrA* results will be included as well as subjects with wild-type only infections. For each subject, all infected sites (whether the infection is wild-type or unknown) will be considered in determining the subject's cure status. Next, the primary analysis will be repeated in the alternate PP population described in Section 6.3.2.3. See Table 10.

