14. TECHNICAL DETAILS

SAS version 9.4 or above will be used to generate all tables, figures, and listings.

**15. SUMMARY OF CHANGES IN THE CONDUCT OF THE STUDY OR
PLANNED ANALYSES**

There are no changes in the planned analyses.

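### The SAP's primary PP analysis ignores culture-positive throats of unknown gyrA, against its own definition of cure, and its gyrA conditions leave PP outside micro-ITT and Visit 1 mutants in ITT only, with no change declared.

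*SAP*

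**What the plan says.** **Outcome.** Protocol 11.4.3.1 and SAP 3.3.2 define the primary outcome alike. Cure needs a negative Visit 2 culture at every site that was positive at Visit 1. Failure is *N. gonorrhoeae* "detectable by culture from at least one anatomical site that had detectable" infection at Visit 1.

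**Protocol populations (11.4.1).** Micro-ITT is every enrolled subject with the organism "isolated from the rectum or urogenital site on Day 1 culture". PP uses the same culture condition and adds eligibility, compliance, evaluability and timing. Neither names a Visit 1 gyrA result. The assay enters through inclusion 3 and exclusion 9, on a specimen taken within 30 days of enrollment.

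**SAP populations.** SAP 3.3.1 ties wild type to the Visit 1 swab, and SAP 6.3.2.2 and 6.3.2.3 require a wild-type Day 1 isolate.
- Micro-ITT: "Subjects with infections at multiple anatomic sites must be wild-type at each culture-positive site to be included in the primary analysis". There is no exception.
- PP: a subject infected at several sites qualifies if wild type at each culture-positive site, or if wild type at the rectal or urogenital site with an unknown throat result. In the second case, "For subjects who meet the second criteria above, the pharyngeal results will be ignored in the determination of cure status".

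**Sensitivity analyses (SAP 8.1.1).** Modified micro-ITT and PP populations bring in "subjects with culture-positive but unknown (indeterminate or missing", that is, unknown gyrA results, and count all infected sites. Mutant results are not brought in.

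**Reporting.** SAP section 15 states: "There are no changes in the planned analyses".

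**The concern.** The PP cure rate carries the formal test. If a culture-positive throat is set aside, a subject who is still infected at Visit 2 can be counted as cured in the result that decides the trial. The case is foreseeable. Protocol 7.1 runs gyrA only when NAAT is positive, so a throat that is culture positive and NAAT negative has a missing gyrA result by design.

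PP is normally a subset of the intent-to-treat set it refines. Here some PP subjects are outside micro-ITT, so a difference between the two results cannot be read as the effect of protocol adherence.

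The study exists to validate the assay clinically (protocol 11.1). Subjects are dosed at Visit 1 once swabs are taken (protocol 7.1), so it is reasonable to infer that the earlier wild-type result led to treatment. Setting aside treated subjects whose Visit 1 result is mutant may remove some of the disagreements that a validation study should show.

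**Working it through.** **1. The plan's own figures.** Inputs from protocol 11.2: the interval is "computed using a one-sided modified Jeffreys interval using a significance level of 0.05"; power is computed "assuming a 98% microbiological cure rate"; the threshold is 0.95; the PP target is 257. With X cures in N, the lower bound is the 0.05 quantile of Beta(X + 0.5, N − X + 0.5). Protocol 11.4.3.1 prints the 0.95 quantile; only the 0.05 quantile is a lower bound, and it reproduces the stated power.

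- 250/257 (7 failures): lower bound 0.9519, pass.
- 249/257 (8 failures): lower bound 0.9470, fail.
- Power = P(at most 7 failures in 257 at 2%) = 85.4%; stated, about 85%.
- N = 195: 80.2%; stated, 80%.
- Enrollment = 257/(0.75 × 0.90) = 380.7, so 381, as stated.
- P(pass) at a true cure rate of exactly 95% is 5.4%.

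The stated figures reproduce. The decision turns on 7 against 8 failures.

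**2. Effect of the throat rule.** Take a subject who is wild type at the rectum, with a culture-positive throat of unknown gyrA at Visit 1. A positive site is taken as enough for failure.

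| Visit 2 rectum | Visit 2 throat | SAP 3.3.2 | SAP 6.3.2.3 |
|---|---|---|---|
| negative | negative | cure | cure |
| negative | positive | failure | cure |
| negative | not available | non-evaluable | cure |
| positive | any | failure | failure |

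No row moves the other way. With 8 failures by the all-sites definition, one of them in the throat only, the rule reports 7 and the test passes.

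**3. Illustration under assumed inputs.** The documents give neither the share *u* of PP subjects with such a throat nor its failure probability *q*. Assume *u* from 2% to 10%, *q* from 5% to 20%, and throat failure independent of the other sites. Let the true all-sites cure rate be exactly 0.95. The rate seen when throats are ignored is then 0.95/(1 − *uq*), and P(pass) at N = 257 is:

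| | *q* = 5% | *q* = 10% | *q* = 20% |
|---|---|---|---|
| *u* = 2% | 6.2% | 7.0% | 9.0% |
| *u* = 5% | 7.5% | 10.2% | 18.2% |
| *u* = 10% | 10.2% | 18.2% | 47.0% |

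These compare with 5.4% when all sites count. The table shows sensitivity to the rule and is not an estimate.

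**4. Membership.**

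| Visit 1 gyrA (culture-positive sites) | Protocol micro-ITT | SAP micro-ITT | SAP PP | SAP 8.1.1 modified sets |
|---|---|---|---|---|
| Rectum wild type, throat unknown | in | out | in, throat ignored | in, throat counted |
| Rectum mutant | in | out | out | out |
| Rectum wild type, throat mutant | in | out | out | out |

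The first row breaks the nesting. Subjects in the last two rows are in no culture-positive population for the primary outcome, though in the last row the rectal infection stays in the rectal site-specific sets. ITT keeps them all. SAP Tables 12 and 15 have mutant rows at Visit 1, so the plan provides for such results.

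**5. Table 4.** It gives no gyrA reason for exclusion from micro-ITT or PP. It lists failed eligibility as a micro-ITT exclusion, which neither SAP 6.3.2.2 nor the protocol contains.

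**The case against.** **Wild type is the target population.** The outcome measure concerns subjects infected with the serine 91 genotype, Visit 1 samples are taken to verify infection, and the protocol leaves detail to the SAP. This has force: whether the screening or the Visit 1 result defines the target is an estimand choice. It does not explain why a Visit 1 culture-positive throat drops out of an outcome that counts every such site.

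**Exclusion 9 may already remove mutants from PP.** It bars a mutant result at any site on a specimen within 30 days of enrollment, and the Visit 1 specimen can be read as such. Then the protocol PP drops these subjects too. This stands for PP. The protocol micro-ITT has no eligibility condition, so the conflict there remains on either reading.

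**The ignored throats are disclosed and re-examined.** SAP 8.1.1 counts them in its modified PP. That is true, but only as a sensitivity analysis, and that analysis also admits subjects whose rectal or urogenital gyrA is unknown, so it does not isolate the throat rule.

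**Listings cover the gaps.** Table 6 counts culture-positive wild-type subjects, and the exclusions listing gives reasons. But that listing must use the population table's wording, which has no gyrA reason.

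Three stronger readings are tempting and are not supported.
- *Mutants vanish from every SAP 8.1.1 analysis.* Table 9 includes ITT, which keeps them.
- *The assay's misclassifications are deleted.* A mutant repeat may be a new infection, wild-type infections with culture-resistant isolates stay in PP, and Tables 12 and 15 report mutants.
- *The extra exclusions break the 80% power.* That needs a further loss of about 4% or more, which no document gives. At 4%, 381 × 0.75 × 0.90 × 0.96 = 246.9. N = 246 gives 77.5%, but every N from 247 to 256 gives 85.6% to 87.5%. SAP section 5 also ties its 10% allowance to the section 6.3 exclusions, and 381 is called approximate.

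**Conclusion.** The concern holds in this form. The throat exception in SAP 6.3.2.3 contradicts the outcome definition in SAP 3.3.2 and protocol 11.4.3.1. For the subjects it covers, it can only raise the primary cure rate. PP is not a subset of micro-ITT. SAP 6.3.2.2 adds a Visit 1 wild-type condition that the protocol micro-ITT lacks, so treated subjects who are mutant at Visit 1 are left in ITT alone for the primary outcome. ITT is a poor substitute, because it includes culture-negative subjects and counts non-evaluable outcomes as failures. For PP, the mutant point depends on how exclusion 9 is read. Section 15 and Table 4 do not reflect any of this.

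One ignored throat failure is enough to change the conclusion when the all-sites count is 8 in 257. How likely that is cannot be fixed from the documents. The sample size arithmetic is sound.

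**What to change.** 1. In the primary PP analysis, count every Visit 1 culture-positive site in cure status. Move the version that ignores a throat of unknown genotype to SAP 8.1.1.
2. Apply the same rule for unknown gyrA in micro-ITT and PP, so that PP is nested.
3. Restore the protocol micro-ITT (rectal or urogenital Day 1 culture positive, whatever the Visit 1 gyrA result), or at least add it to SAP 8.1.1.
4. State whether exclusion 9 covers the Visit 1 specimen. That settles whether Visit 1 mutants belong in PP.
5. Add a gyrA exclusion reason to Table 4, reconcile its micro-ITT eligibility row with the text, and record the departures from the protocol in section 15.

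The cost is SAP wording and a few table rows, with no new data. The primary cure rate may come out slightly lower.

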4.4.5. Blinding

Not applicable. This is an unblinded study.

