5. SAMPLE SIZE CONSIDERATIONS

The primary analysis will compute the proportion of ciprofloxacin-susceptible *N. gonorrhoeae*-infected subjects with microbiological cure 5-10 days after receiving ciprofloxacin in the per-protocol analysis population. The confidence interval for the microbiological cure proportion will be computed using a one-sided modified Jeffreys interval using a significance level of 0.05. Power calculations were performed via a simulation study based on 10,000 replications assuming a 98% microbiological cure rate.

Figure 1 presents the power available to test that the microbiological cure rate is at least 95% (i.e., lower bound of the one-sided confidence interval is at least 95%) across a range of evaluable sample sizes. Here, evaluable denotes eligible for the PP analysis population. The power reaches 80% at a sample size of 195 evaluable subjects; however, since the power curve is not monotonic, sample sizes directly on either side of 195 are below 80%. Since the exact number of evaluable subjects at the end of the study is difficult to predict, an evaluable target of 257 subjects is chosen to ensure at least 80% even if the exact number of evaluable subjects at the end of the study differs slightly from 257. With a target of 257, the power available is approximately 85% and we can fall at most 10 subjects short (sample size of 247 evaluable subjects) and still ensure 80% power. Any sample size greater than 257 will ensure at least 80% power.

To calculate the number of subjects required to enroll to reach 257 subjects in the PP analysis population, the following assumptions are made:

- 25% of enrolled subjects will be culture negative at baseline.
- 10% of subjects will be excluded from the PP analysis population (reasons for exclusion are stated in Section 6.3)

Under these assumptions, enrolling 381 subjects will provide 257 subjects in the PP analysis population. Since the proportion of subjects who will be culture negative at baseline can vary depending on a number of factors, 25% is a rough estimate. The exact number of subjects needed to provide 257 subjects in the PP analysis population may vary from 381, so 381 is an approximate enrollment target.

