6. GENERAL STATISTICAL CONSIDERATIONS

6.1. General Principles

Tabulations will be used extensively to summarize the data. All continuous variables will be summarized using some or all of the following descriptive statistics: n (samples size), mean, standard deviation, median, maximum, and minimum. The frequency and percentages (based on the sample size) of observed levels will be reported for all categorical measures. Modified Jeffreys confidence intervals (CIs) for binomial proportions will be computed for efficacy variables [2]. A 5% one-sided significance level will be used; i.e. one-sided 95% confidence intervals will be generated. In general, all data will be listed, sorted by site and subject, and when appropriate by visit number within subject. All summary tables will be annotated with the total population size relevant to that table, including any missing observations.

Note that in the data listing, Subject ID is the unique subject identifier, not the Study ID used on study, and dates will not be included, only Study Day. Study Day 1 will be the day of the dose of treatment.

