6.1.1. Pseudo Code

The following SAS® pseudo code will be used to calculate the following:

Lower bound of the one-sided 95% Jeffreys CI for proportions/percentages if the number of cures is less than the number of subjects included in the analysis:

```
proc freq;  
    tables cure / alpha=0.1 binomial(jeffreys);  
run;
```

Lower bound of the one-sided 95% Jeffreys CI for proportions/percentages if the number of cures is equal to the number of subjects (n) included in the analysis:

```
CI_Lower = 0.05** (1/n);
```

95% Wilson CI for proportions/percentages:

```
proc freq;  
    Table treatment*analysisvariable / alpha=0.1 binomial(wilson);  
    ods output binomialcls=outputdsn;  
run;
```

95% Exact Blaker CI for proportions/percentages:

```
proc freq;  
    Table treatment*analysisvariable / alpha=0.1 binomial(blaker);  
    ods output binomialcls=outputdsn;  
run;
```

95% Agresti-Coull CI for proportions/percentages:

```
proc freq;  
    Table treatment*analysisvariable / alpha=0.1 binomial(AC);  
    ods output binomialcls=outputdsn;  
run;
```

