8. EFFICACY EVALUATION

8.1. Primary Efficacy Analyses

The primary analysis will test whether the microbiological cure rate of ciprofloxacin in subjects infected with *gyrA* serine 91 genotype *N. gonorrhoeae* at rectum or urogenital site is greater than or equal to 95%. The cure rate will be estimated by the proportion of subjects infected with *gyrA* serine 91 genotype *N. gonorrhoeae* with microbiological cure at Visit 2. The microbiological outcome status is defined in Section 3.3.2.

A formal hypothesis test will be performed with null hypothesis that the proportion of ciprofloxacin-susceptible (as identified by the *gyrA* assay) *N. gonorrhoeae*-infected subjects with microbiological cure 5-9 (or 10) days after receiving ciprofloxacin is less than 0.95 and alternative hypothesis that the proportion is at least 0.95. The test will be performed by calculating the one-sided 95% modified Jeffreys confidence interval and comparing it to the value 0.95.

The summary of microbiological cure number, microbiological cure rate, and one-sided 95% modified Jeffreys confidence interval by analysis population will be presented (Table 8). See Section 6.1.1 for pseudocode to fit the above analyses. Individual efficacy data is presented in Listing 7.

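### Exclusions from the alternate per-protocol sensitivity population are decided case by case with no masking to outcome, which weakens that row of Table 10 as a robustness check

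*SAP*

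**What the plan says.** Protocol 11.4.1 announces alternate PP analyses and leaves their details to the SAP. SAP 6.3.2.3 repeats the protocol's categories: concomitant infection, disease, procedure or medication that might interfere with the product; significant protocol deviations; and a catch-all for other events that might affect effectiveness or the analyses. It adds one operating rule: "Exclusions from this alternate PP population will be determined on a case-by-case basis prior to database lock". Neither document says who decides or what they may see.

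SAP 8.1.1 gives the population its use: "the primary analysis will be repeated in the alternate PP population", reported in Table 10 as a sensitivity analysis of the primary outcome. The primary analysis itself uses the main PP population, which is defined by stated rules (Protocol 11.4.3.1; SAP 6.3.2.3).

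On knowledge of outcomes, SAP 4.4.5 states "This is an unblinded study". Protocol 7.3 has test-of-cure results phoned to subjects at Visit 3 (Day 11-14), and SAP 6.2 places the final analysis after lock, once all subjects have been followed through Visit 3. The only separation from outcome data is the independent statistician in SAP 6.6, whose task is the futility count.

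**The concern.** In a blinded randomised trial, settling exclusions before lock normally means settling them before outcomes can be compared by arm. That protection is absent here. There is one arm, the outcome is each subject's own Visit 2 culture, and it is known at the site well before lock.

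A treatment failure is also the case most likely to prompt a search for an explanation. Re-exposure is one example: interim sexual history is taken at Visit 2 (Protocol 7.2), and SAP 8.3 already analyses cure by re-exposure. The catch-all category is wide enough to admit such a subject as an exclusion after the result is seen, while a cured subject with the same history may never be reviewed.

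At stake is the value of the sensitivity analysis. If its exclusions can depend on outcome, a favourable alternate PP bound adds little support to the primary result.

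**Working it through.** **Inputs**
- Error level (SAP 6.1): "A 5% one-sided significance level will be used; i.e. one-sided 95% confidence intervals will be generated".
- Decision rule (SAP 8.1): "The test will be performed by calculating the one-sided 95% modified Jeffreys confidence interval and comparing it to the value 0.95".
- Interval (SAP 6.1.1): "tables cure / alpha=0.1 binomial(jeffreys". A two-sided alpha of 0.1 puts 5% in each tail, so the lower bound for X cures in N subjects is L(X, N) = 5% quantile of Beta(X + 0.5, N - X + 0.5). Protocol 11.4.3.1 prints the 0.95 quantile instead; the 5% quantile matches the SAP code, reproduces the planned power, and is used here.
- Planning values (SAP 5): "assuming a 98% microbiological cure rate", and "an evaluable target of 257 subjects is chosen to ensure at least 80"% power.

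**1. Reproduce the plan's figure.** At N = 257:
- 7 failures: L(250, 257) = 95.19%, meets 95%.
- 8 failures: L(249, 257) = 94.70%, does not.

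The rule is therefore at most 7 failures. Power = P(Bin(257, 0.02) ≤ 7) = 85.4%, against about 85% in the SAP. At N = 195 the same method gives 80.2%, with 194 and 196 below 80%, again as the SAP says.

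**2. Exclude failures.** An exclusion lowers both the failure count and N.

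| Start at N = 257 | Failures excluded | Remaining | Lower bound |
|---|---|---|---|
| 8 failures | 1 | 7 in 256 (249 cures) | 95.18% |
| 9 failures | 2 | 7 in 255 (248 cures) | 95.16% |

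Both cross the threshold.

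**3. How often would one exclusion matter at N = 257?** Only when there are exactly 8 failures:

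| True cure rate | P(exactly 8 failures) |
|---|---|
| 98% | 7.1% |
| 97% | 14.1% |
| 96% | 10.7% |
| 95% | 4.7% |

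**4. Does it hold at other sample sizes?** At N = 247, the shortfall that SAP 5 tolerates, 7 failures just pass (95.00%) and 8 miss (94.49%). Excluding one of the 8 leaves 7 in 246, L = 94.98%, still a miss. From N = 200 to 300, excluding one failure from the first failing count produces a crossing at every N except 221, 247, 273 and 299.

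**5. Upper limit.** Suppose one failure could always be excluded at N = 257. The chance that the alternate PP bound reaches 95% would be:
- true rate 95%: 5.4% + 4.7% = 10.1%;
- true rate 98%: 85.37% + 7.07% = 92.4%.

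These are ceilings, because they assume that a failing subject with a qualifying event is always available.

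**The case against.** The strongest reply is that no decision rests on this analysis. The formal test is in the rule-based PP population, and neither document attaches a success criterion to Table 10. If the primary analysis misses, an alternate PP bound above 95% does not reverse it; if it passes, there is no miss to rescue. The micro-ITT and ITT results, which count non-evaluable subjects as failures, stand beside the primary result in Table 8. All of this stands. A reader might infer from the one-failure crossing that the trial's verdict can be turned; the documents do not support that.

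A reader might also infer that the people deciding exclusions will see the outcomes. The documents do not say so, because they name no decider. What they support is narrower: no masking is specified, and results are available before lock.

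Three further limits are fair:
- Any discrete rule has a count at which one event matters, so the crossing shows scale and does not measure bias.
- The main PP definition already removes eligibility violations, non-compliance, contraindicated medication, other systemic antibiotics and out-of-window visits, so fewer failures remain open to exclusion.
- If the alternate PP population is a subset of the main PP population, subtracting Table 10 from Table 8 gives the numbers of excluded cures and failures. Listings 3, 7 and 17 carry subject-level deviations, outcomes and medications.

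The last point does not tell a reader which subjects were excluded from the alternate population or why. Table 4 covers ITT, micro-ITT and PP only, and the shell for the listing of excluded subjects gives only those three as examples. Nor does any of these points supply the missing masking.

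**Conclusion.** The point holds as a low-cost improvement. The SAP's rule for alternate PP exclusions does not protect against outcome-driven selection in this design, and the detail that the protocol deferred to the SAP is not there. The consequence is confined to the alternate PP row of Table 10.

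Near the threshold the effect can be one subject: 94.70% becomes 95.18% at N = 257. That requires exactly 8 failures, one of them with an event that fits the alternate categories and was not already excluded from the main PP population. The probabilities above assume independent subjects and exactly 257 evaluable. Nothing in the documents shows that exclusions would in fact follow outcomes; the plan simply does not prevent it.

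**What to change.** Replace the case-by-case sentence in SAP 6.3.2.3 with text such as:

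> Exclusions from the alternate PP population will be decided and signed off before database lock from deviation, medical history and medication listings that omit all Visit 2 culture, NAAT and *gyrA* results, by reviewers working only from those listings.

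Extend the listing of excluded subjects (Listing 2 in SAP Appendix 3) to cover the alternate PP population, giving the reason and the microbiological outcome for each exclusion. The outcome column is filled in after sign-off.

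The cost is one masked listing, plus the constraint that site staff who know a subject's result should not make the decision. Protocol 15.2 describes endpoint data entered in the same system as clinical data, so the listing has to be produced with the result fields left out. Trial conduct, the primary analysis and the sample size do not change.
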